Clinical investigation plan

C19-683

(EX-MKTG-116)

Quantification of the visual benefits of soft toric contact lenses compared to soft spherical contact lenses over a range of refractive astigmatism

**A clinical evaluation for
CooperVision Inc.**

Principal Investigator
[name]

[figure not shown]
April 2020

Contents

Document control	3
Study summary	
Section 1. Overview	6
1.1 Background	6
1.2 Personnel	6
1.3 Study objectives	6
1.4 Study design	6
1.5 Statistical considerations	7
1.6 Risk analysis	7
1.7 Clinical trial registration	7
Section 2. Resources	8
2.1 Subject selection	8
2.2 Subject discontinuation	9
2.3 Safety parameters, adverse events and concurrent illnesses	9
2.4 Study termination	10
2.5 Protocol deviations	10
2.6 Study resources	10
2.7 Study control	11
2.8 Documentation	11
2.9 Data collection and analysis	11
2.10 Study completion	11
2.11 Confidentiality	12
2.12 Study monitoring	12
Section 3. Subject management	13
3.1 Visit scheduling	13
3.2 Visit conduct	13
3.3 Monitoring subject compliance	17
3.4 Missing, unused and spurious data	17
Section 4. Study co-ordination	18
4.1 Document processing	18
4.2 Disclosure	18
4.3 Personnel	18

Appendices

- A Adverse events
- B Randomisation table
- C Grading scales, questionnaires

Study summary

This randomised, crossover, partially masked (for contact lenses), non-dispensing study will compare the clinical performance and subjective acceptance of a custom-made soft toric Biofinity XR contact lens, a soft spherical Biofinity contact lens and a spectacle lens correction, across a range of levels of astigmatism and for three different pupil sizes.

Up to 55 subjects will be enrolled onto this study. At the initial visit, each subject will be fitted with Biofinity spherical and toric contact lenses, in either one or both eyes, depending on whether their astigmatic error falls within the required range. Custom-made Biofinity XR Toric lenses and Biofinity spherical lenses will then be ordered. At visit 2, each subject will wear a spherical Biofinity lens type, a custom-made Biofinity XR Toric lens type and a spectacle correction, in a random sequence for approximately 30 minutes. The optical corrections will be worn in one eye only, with the other eye patched. The following will be assessed throughout the visit: ocular physiology, [REDACTED], high contrast and low contrast visual acuities for three different pupil sizes [REDACTED] If both of the subject's eyes are suitable for the study, they will return for visit 3, where the procedures at visit 2 will be repeated for the other eye. A study summary is shown in Table 1.

V st	Procedures
Int a v st (may be repeated)	Informed consent taken Explanation of study procedures and subject instructions Ocular, medical and contact lens histories Auto-keratometry [REDACTED] visual acuity Biomicroscopy Fitting of toric lenses Visual acuity [REDACTED] Fitting of spherical lenses Visual acuity and over-refraction Custom-made toric and spherical contact lenses ordered Medical or ocular issues since the last visit Entrance biomicroscopy and VA Patching of the eye not being studied Fitting of first randomised lens correction HC and LC visual acuity with different pupil sizes [REDACTED] Fitting of second randomised lens correction HC and LC visual acuity with different pupil sizes [REDACTED] Fitting of third randomised lens correction HC and LC visual acuity with different pupil sizes [REDACTED] Exit biomicroscopy and VA Payment issued (if visit 3 not applicable)
V st 2 (first eye evaluation) (may be repeated)	Medical or ocular issues since the last visit Entrance biomicroscopy and VA Patching of the eye not being studied Fitting of first randomised lens correction (in the other eye to that used at Visit 2) HC and LC visual acuity with different pupil sizes [REDACTED] Fitting of second randomised lens correction HC and LC visual acuity with different pupil sizes
V st 3 (if applicable) (second eye evaluation) (may be repeated)	Medical or ocular issues since the last visit Entrance biomicroscopy and VA Patching of the eye not being studied Fitting of first randomised lens correction (in the other eye to that used at Visit 2) HC and LC visual acuity with different pupil sizes [REDACTED] Fitting of second randomised lens correction HC and LC visual acuity with different pupil sizes

	Fitting of third random sed lens correct on HC and LC visual acuity with different pupil sizes [REDACTED]	
	Examination and VA Payment issued	

Table 1: Study summary.

Section 1. Overview

1.1 Background

In some contact lens markets, the use of soft toric lenses is significantly lower than might be expected for the range of astigmatism in the population. The reasons for this are varied, but appear to include practitioner reluctance to fit and prescribe such lenses due to a perception of a limited clinical benefit in doing so. This study seeks to provide clinical data to highlight the benefits of prescribing soft toric lenses to astigmats.

1.3 Study objectives

The aim of this work is to undertake a range of vision-related measures with soft toric contact lenses (custom-made Biofinity XR Toric), soft spherical contact lenses (Biofinity) and spectacle lens correction across a range of levels of astigmatism, seven intervals from 0.00DC to -1.50DC, and for three different pupil sizes. Pupil size will be controlled using a novel, automated room lighting/feedback system. This will lead to a quantification of the visual benefit of torics vs. spheres, and allow for the identification of the astigmatic threshold where the difference between these two lens designs becomes clinically meaningful.

1.4 Study design

This will be a randomised, crossover, partially subject-masked (for contact lenses only), non-dispensing study, controlled by cross-comparison. Many subjects will have both eyes within the astigmatism range, and data from two eyes for these subjects will be in the analysis. Some subjects may only have one eye in range. Subjects with two suitable eyes will attend for three visits and those with only one suitable eye will attend for two visits. At the initial study visit, up to 55 subjects will be fitted with the toric (Biofinity XR toric) and spherical (Biofinity) contact lenses in order to provide 12 eyes in each of the seven cylinder powers studied (0.00 to -1.50DC). At visit 2, each subject will wear the spherical contact lens, custom-made toric contact lens and spectacle correction, in a randomised sequence. Visual acuity will be assessed for three different pupil sizes [REDACTED]

[REDACTED] using the novel automated room lighting/feedback system. [REDACTED]

[REDACTED] During clinical evaluation the eye which is not being studied will be patched. For subjects with both eyes within the required astigmatism range, they will return for visit 3, where the procedures undertaken at visit 2 will be repeated on the fellow eye.

1.5 Statistical considerations

The principal hypothesis to be tested in this work is that visual acuity [REDACTED] for the different lens corrections and pupil sizes will be the same.

Visual acuity assessment, biomicroscopy gradings [REDACTED] will generate data that are likely to be continuous and normally distributed. As such, these will be compared using linear regression models or other parametric methods. [REDACTED]

[REDACTED] Deviations may be necessary due to differences between the actual data distribution compared with the anticipated data distribution.

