1.5.1 Power analysis

An *a priori* power analysis has determined that 12 eyes are required for each 0.25DC level of astigmatism to provide 80% power to detect a meaningful difference of 0.1 logMAR units between correction types. To evaluate the seven intervals from 0.00DC to -1.50DC, 84 eyes are required.

This analysis assumes a two-tailed paired analysis and an alpha of 0.05. To allow for discontinuations, up to 55 subjects will be fitted with the study lenses.

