2.7 Study control

This study is controlled by cross-comparison. Bias will be minimised by randomising the order of assessment. Subjects will be masked to the two contact lens types (toric versus spherical) – contact lenses will be over-labelled.

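### Does the three-correction crossover need a period term named in its visual acuity model?

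*Combined protocol and SAP*

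**What the plan says.** Section 1.4 sets out the crossover: "At visit 2, each subject will wear the spherical contact lens, custom-made toric contact lens and spectacle correction, in a randomised sequence". Subjects with two suitable eyes repeat this on the fellow eye at visit 3, and both eyes count: "Many subjects will have both eyes within the astigmatism range, and data from two eyes for these subjects will be in the analysis". The Study summary says the corrections are worn "in a random sequence for approximately 30 minutes", without making clear whether that is the time for each correction or for all three.

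Order is dealt with in section 2.7: "Bias will be minimised by randomising the order of assessment". The contents page lists a randomisation table as Appendix B; it is not in the public file.

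Section 1.5 gives the analysis in one sentence, "As such, these will be compared using linear regression models or other parametric methods", and redacted text follows at once. Section 1.5.1 gives the sizing: "12 eyes are required for each 0.25DC level of astigmatism to provide 80% power to detect a meaningful difference of 0.1 logMAR units", and "This analysis assumes a two-tailed paired analysis and an alpha of 0.05". Neither a standard deviation nor an expected order effect is stated.

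**The concern.** The three corrections follow one another in a single sitting, and each brings many acuity readings. Section 3.2.3 gives three at step 6 (high contrast before over-refraction, then high and low contrast with it) and six at step 11 (two contrasts at three pupil sizes). That is 9 per correction and 9 × 3 = 27 per eye. Practice or fatigue could shift acuity between the first and the third correction.

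A crossover analysis often carries a period effect for this reason, and the visible model sentence names none. With only 12 eyes per cylinder level, chance can leave the toric lens tested earlier than the sphere more often than later within a level. Any drift would then add noise to the comparison that is meant to "allow for the identification of the astigmatic threshold where the difference between these two lens designs becomes clinically meaningful". At stake would be some of the 80% power per level, and a choice left to the analyst.

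**Working it through.** **1. The plan's own figure.** Inputs from section 1.5.1: 12 eyes per level, difference 0.1 logMAR, two-sided alpha 0.05, paired, 80% power; 7 × 12 = 84 eyes. The standard deviation (SD) of the paired difference is not given, so 12 cannot be checked independently, only inverted. Solving the noncentral t (11 df) for 80% power at 0.1 / (SD/√12) gives SD = 0.1125. An SD of 0.1066 would already allow 11 eyes, and the normal approximation gives 0.1 × √12 / (1.960 + 0.842) = 0.1236. The assumed range is therefore 0.107 to 0.124.

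**2. Does order bias the comparison?** Over the six possible orders, the toric position minus the sphere position is −2, −1, −1, 1, 1, 2. The mean is 0, so a drift common to all eyes cancels in expectation under randomised order. Simulated type I error under simple randomisation was 4.6-5.3%, with or without a period term.

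**3. How much noise could order add?** The variance of those positions is (4 + 1 + 1 + 1 + 1 + 4)/6 = 2. A linear drift of g logMAR per period therefore adds 2g² to the variance of the difference, and the total SD is √(0.1125² + 2g²). No passage gives g; the values below are assumptions. The paired test uses 11 df. The pooled regression over all eyes and corrections uses 252 − 84 − 14 = 154 df (observations, eye effects, correction-by-level effects).

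| Drift per period | Added variance | Total SD | Paired power, no period term | Pooled power, no period term |
|---|---|---|---|---|
| 0 | 0% | 0.1125 | 80.0% | 86.4% |
| 0.01 | 1.6% | 0.1134 | 79.4% | 85.9% |
| 0.02 | 6.3% | 0.1160 | 77.6% | 84.3% |
| 0.03 | 14.2% | 0.1203 | 74.6% | 81.7% |
| 0.04 | 25.3% | 0.1259 | 70.7% | 78.0% |

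At SD 0.1236 the pooled figure is already 79.5% with no drift, and 77.5% at 0.02; at SD 0.1066 it is 89.8% and 87.7%. The loss at 0.02 is about 2 points throughout.

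**4. What would the term cost?** Fitted jointly over 84 eyes, period takes 2 df (154 to 152). Under simple randomisation the mean variance inflation is 1.013, and pooled power goes from 86.4% to 86.0%. With orders balanced within each level the cost is 0.01 point. This is an average: in single levels with an unlucky order the 95th percentile of the loss is 1.4 points and the largest simulated loss 4.6. The term breaks even at a drift of about 0.01.

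**5. If the planning SD already contains order noise.** The drop in the table does not then arise. The plan has its 80%, and a period term would raise it: with SD √(0.1125² − 2g²), paired power is 80.6, 82.5, 85.6 and 89.9% at drifts of 0.01 to 0.04.

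**6. Can absence be shown?** The place where model terms would be listed is redacted, and the table that would show whether orders are balanced is not supplied. Neither can be counted as missing from the plan.

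**The case for a change.** The best case for raising the point is that the remedy is cheap. A jointly estimated period term needs no extra eyes, visits or procedures, its average cost is about half a point of pooled power, and it protects against a loss of about 8 points (86.4 − 78.0) at a drift of 0.04. Under the paired test without the term, 13, 14 or 15 eyes per level would be needed to regain 80% at drifts of 0.02, 0.03 and 0.04. Naming the term in advance would also close an analyst's choice, and the choice is not wholly idle: in a three-correction model, fitting period separately within each 12-eye level costs about 4 points on average under simple randomisation.

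This arithmetic stands. Its force does not, for three reasons:

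- The larger gains need a drift of 0.04 per period, which is 2 × 0.04 = 0.08 logMAR from the first correction to the third, close to the 0.1 that the trial treats as meaningful. Nothing in the documents points to drift of that size, and the readings at the initial visit, on entry and at step 6 give practice before the pupil-size measurements.
- The steeper losses belong to the paired test, which the visible text names only for sizing; section 1.5 names regression first.
- The term would remove only an additive drift shared by all eyes. It would not remove carryover or eye-specific fatigue, nor the extra testing when a toric lens is replaced for misalignment (section 3.2.3, step 8).

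**Conclusion.** The concern does not hold. Order is controlled by randomisation, so the toric-sphere comparison is unbiased and its error rate is close to 5% without a period term. The documents cannot show that the term, or balanced orders, is absent. Even if it were absent, the effect is on precision alone: nothing at zero drift, about half a point at 0.01, about 2 points at 0.02, and pooled power still above 80% through 0.03. Only at 0.04 does it fall below, to 78.0%.

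These sizes assume an SD of 0.1125, a linear drift common to all eyes, complete data, independent residuals with equal variance across levels, and a planning SD free of order noise. At SD 0.1236 the pooled figure is just under 80% with no drift at all, so that shortfall is not a matter of order. Including period is sensible practice that an analyst of a crossover can adopt within the regression the plan already allows; not seeing it named does not put the plan's conclusions at risk.

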1.5.1 Power analysis

An *a priori* power analysis has determined that 12 eyes are required for each 0.25DC level of astigmatism to provide 80% power to detect a meaningful difference of 0.1 logMAR units between correction types. To evaluate the seven intervals from 0.00DC to -1.50DC, 84 eyes are required.

This analysis assumes a two-tailed paired analysis and an alpha of 0.05. To allow for discontinuations, up to 55 subjects will be fitted with the study lenses.

1.6 Risk analysis

This study is considered to be a non-significant risk study based on United States Food and Drug administration (FDA) and International Standards Organization (ISO) guidelines due to the daily wear nature of the study and non-invasive study procedures. Subjects may not benefit directly from taking part in this study; however, information from this study may help researchers gain new insights about contact lens wear and to help others in the future. With the potential benefit of this study, the work is considered to be ethically justifiable. Ethical approval will be sought from the University of Manchester Senate Committee on the Ethics of Research on Human Beings (hereafter referred to as Manchester UREC). The work where practical will be conducted in accordance with the ICH Good Clinical Practice Guidelines and the international standard BS EN ISO 14155:2011 'Clinical investigation of medical devices for human subjects'.

1.7 Clinical trial registration

This study will be registered with clinicaltrials.gov in accordance with section 801 of the Food and Drug Administration (FDA) Act which mandates the registration of certain clinical trials of drugs and medical devices.

Section 2. Resources

2.1 Subject selection

In this work, up to 55 subjects will be fitted with the study lenses, with the aim of 84 eye evaluations completing the study (12 per cylinder power in 0.25DC steps, from 0.00 to -1.50DC).

2.1.1 Subject withdrawal and replacement

This study includes three clinical visits (two clinical visits if only one eye is suitable). Once the study consent form is signed, the subject is considered to be enrolled on the study. Subjects who have signed the consent form, but who have not completed the initial visit will usually be replaced. All subject data will be included in the final analyses unless there are strong grounds for exclusion; such grounds will be detailed in the final report.

2.1.2 Subject recruitment

Subjects will be recruited by one or more of following means:

1. Posting study details on The University of Manchester's 'Research Volunteers' website.
2. Correspondence to existing wearers on the Eurolens Research database of subjects.
3. Advertising through a variety of media via a format separately approved by Manchester UREC.

2.1.3 Inclusion criteria

Subjects will only be eligible for the study if:

1. They are of legal age between 18 and 40 years.
2. They understand their rights as a research subject and are willing and able to sign a Statement of Informed Consent.
3. They are willing and able to follow the protocol.
4. They are current wearers of any soft contact lens (i.e. have worn lenses in the last six months).
5. They have refractive ocular astigmatism between 0.00DC and -1.50DC in one or both eyes.
6. They have a spherical component to their ocular refractive error between 0.00 and -6.00 DS.
7. They could attain at least 0.10 logMAR distance high contrast visual acuity in one eye with the study lenses within the available power range.
8. They can be fitted satisfactorily with both lens types.
9. They own an acceptable pair of spectacles.
10. They agree not to participate in other clinical research for the duration of this study.

2.1.4 Exclusion criteria

Subjects will not be eligible to take part in the study if:

1. They have an ocular disorder which would normally contra-indicate contact lens wear.
2. They have a systemic disorder which would normally contra-indicate contact lens wear.
3. They are using any topical medication such as eye drops or ointment.
4. They have had corneal refractive surgery.
5. They have any corneal distortion resulting from previous hard or rigid lens wear or have keratoconus.
6. They are pregnant or breastfeeding.
7. They have any ocular abnormality which would, in the opinion of the investigator, normally contraindicate contact lens wear.
8. They have an amblyopic eye, in which case only dominant eye will be assessed for that subject.
9. They have an infectious disease (e.g. hepatitis), any immunosuppressive disease (e.g. HIV) or diabetes.
10. They have a history of severe allergic reaction or anaphylaxis.
11. They have taken part in any other contact lens clinical trial or research, within two weeks prior to starting this study.

2.2 Subject discontinuation

In general, subjects should be discontinued at any time, if it is in their best interests, as judged by the investigator. Reasons for this may include clinical signs of grade 3 or more, lack of motivation, discomfort, or repeated refusal to follow instructions. Subjects will be discontinued if a serious adverse event occurs or if they miss two or more planned consecutive visits. Subjects who fail to satisfy all the inclusion and exclusion criteria will be discontinued and replaced. Subjects may choose to leave the study at their own request. All discontinuations will be carefully recorded.

2.3 Safety parameters, adverse events and concurrent illnesses

The key safety parameters are the serious and significant ocular adverse events [REDACTED]

Clinical assessment is made at the study visit(s) for these parameters. The presence of an adverse event will be reported on the case report forms and those described as 'serious' or 'significant' will be detailed in the final report. Similarly, any concurrent illness that is likely to impact on the relevance and quality of the captured data will be noted on the case report form.

2.3.1 **Investigator obligations**

At all times the investigator will act in the best interest of the subject. Referral or treatment of an adverse event or other clinical finding should be initiated in the best clinical judgement of the investigator, irrespective of the participation in the clinical study.

2.3.2 **Reporting obligations**

In the case of a 'serious' or 'significant' adverse event, the Principal Investigator will notify the Industrial Contact Person as soon as possible. Manchester UREC and any regulatory authorities will be informed as required.

2.4 **Study termination**

If it becomes necessary to terminate the study earlier than planned, the Industrial Contact Person will notify the Principal Investigator who will end the study with the cooperation of other staff members. Manchester UREC will be informed.

2.5 **Protocol deviations**

Any deviations from this protocol will be recorded and reported to the Industrial Contact Person as appropriate. Manchester UREC will be informed as necessary.

2.5.1 **Protocol amendments**

Any amendments will be agreed between the Industrial Contact Person and the Principal Investigator with the cooperation of other staff members. Amendments will be recorded, identified and distributed. Approval from Manchester UREC will be obtained as necessary.

2.6 **Study resources**

Study products will be stored according to the manufacturer's product instructions.

2.6.1 **Lenses**

Details of the study lens are provided in Table 2. All lens types are CE marked. Initial lens selection will be as indicated by the manufacturer fitting guidelines.

Name	Biofinity XR Toric	Biofinity Sphere	Biofinity Toric*
Manufacturer	CooperVision Inc	CooperVision Inc	CooperVision Inc
Material	Comficon A	Comficon A	Comficon A
EWC (%)	48%	48%	48%
BOZR (mm)	8.7	8.6	8.7
Diameter (mm)	14.5	14.0	14.5
Spherical powers (DS)	-6.00 to -1.50 (0.25 steps)	-6.00 to -1.50 (0.25 steps)	-6.00 to -1.50 (0.25 steps)
Cylinder powers (DC)	Custom-made	n/a	-0.75 and -1.25

Table 2: Study lenses. *The Biofinity Toric lens is used for trial fitting only.

